The LLM version of KiT is built using 3 components: 1) a web app with a prototype created with the Streamlit Python framework, which will provide the user interface; 2) an instance of AnythingLLM, an open-source application that turns documents into context that the LLM can use for reference during conversations; and 3) a Microsoft Azure OpenAI instance which runs the GPT-4 LLM.

The Streamlit app enables the user to send a query (Fig. 1). The app makes a call to the AnythingLLM API, sending the prompt to a workspace in the AnythingLLM instance. This instance is configured with the required documents that users need to chat with KiT. It is also connected to Microsoft Azure which is running the LLM. Azure returns the answer to the user query to AnythingLLM, which in turn returns the answer to the Streamlit app (Fig. 2).

A knowledge-base of diabetes-related documents comprised of the same resources used in the Q&A feature is used to create the LLM version of KiT. A research associate, research analyst and post-doctoral researcher at the Centre for Digital Therapeutics extracted the content from each resource to create the knowledge base. Each resulting document was then uploaded to AnythingLLM, which turns it into embeddings using OpenAI's text-embedding-ada-002 model (of note, these documents do not contain sensitive data; rather, they have information on diabetes-related topics freely available on the web). When a user makes a query, the embeddings are used by AnythingLLM to return the more relevant documents, which are then sent to the LLM running on Azure as context to create its answer. This minimizes the possibility of incorrect responses while ensuring answers are based on the curated knowledge-base. In addition, answers from the LLM also provide URL links to users (Fig. 1). If no relevant document is found by AnythingLLM, a standard reply is given: "There is no relevant information in this workspace to answer your query".

The Streamlit app and AnythingLLM instance will run on a server set up by MEMOTEXT. Users will be sent an URL to the Streamlit app as an SMS through MEMOTEXT, which will contain their study user ID as a parameter – for example <<https://llmbotlink.ca/?username=1>>. This username parameter in the URL (in this case representing study ID 1) is essential as it will allow us to log conversation history for each user.

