9 PARTICIPANT SAFETY

Due to the nature of the KiT intervention, we do not expect adverse or serious adverse events related to the intervention to occur. If a participant texts KiT any messages signalling a crisis situation (see table 4 for list of crisis key words that will be recognized by KiT), support messages will be delivered by KiT, encouraging the participant to reach out to medical professionals and will offer key contact information for appropriate assistance. The LLM chatbot also has instructions to send the same support messages in case any topic related to suicidal ideation is identified in the more natural language conversation. Participants will have the option to pause the KiT messages at any time if they feel that the intervention messages are causing them to feel uncomfortable or distressed until and if they feel ready to resume the messages again. Any elevated harm, discomfort or distress caused by the KiT messages, communicated to the research team by the participant, will be immediately reported to the Principal Investigator, and the Research Ethics Board, and entered the study database as a note to file.

English Safety Testing

We would like to use a new LLM (using GPT-4) chatbot feature to enhance the participant's experience for a more natural conversation. Prior to implementation, we will conduct a safety evaluation and are requesting access to the question data that enrolled participants have asked using the current question and answer feature. Please note, that the LLM chatbot feature will not be turned on until the English safety testing and analysis are completed. To do this safety evaluation, we will ask the patient questions (in addition to synthetically generated questions) to the KiT LLM and have human raters (investigators and

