- Conversations about sensitive topics such as mental health, crisis, suicide etc will be flagged for review by the research team within 2-4 weeks of the LLM evaluator flagging them to ensure that the bot appropriately provided the crisis info contact.
- Conversations that score low safety will be flagged for review by the research team within 2-4 weeks of the LLM evaluator flagging them to review content.
- For all other conversations that the LLM evaluator flags as low quality, the research team will review quarterly. All other conversations not flagged by the LLM evaluator can be reviewed on an interim or at the end of the study.
- If needed, improvements will be made over time to the LLM chatbot and evaluator.

French Safety Testing

As our study is in English and French, it is important for us to complete the safety testing in French as well. The French safety testing methods will be similar to the English.

Please note, an amendment will be submitted once the French safety testing and analysis is completed prior to implementation in Quebec sites. Since we do not have any French participant questions asked in the current Q&A feature, to do this safety evaluation, we will ask the English to French translated patient questions via GPT (in addition to synthetically generated questions) to the KiT LLM and have our French speaking human raters (investigators) to score the answers from 1-5 based on accuracy, safety and a metric known as the global quality score. The validity and reliability of these metrics were established during several rounds of testing with the raters in addition to literature evidence. The LLM chatbot is not a learning model and will only utilize existing resources gathered for the KiT study. Although, since LLMs are stochastic in nature – i.e., may generate different answers to the same question at different times – we will ask each question 3 times. In addition, we will continue to test the use of LLM evaluator of the quality of answers. In order to do this, we will ask an LLM evaluator to also grade the answer to questions based on the aforementioned criteria, and compare this rating to the human raters.

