	Prompting patient with T1D information from a validated bank of resources	KiT: Hi, I wanted to send you some information about government assistance programs for people living with T1D. The Assistive Devices Program (or ADP) is a government program that may support you with the costs of your diabetes devices. It is something that needs to be renewed each year with the support from your physician. To learn more go to [link] or ask your physician about it at your next appointment.
PREMs/PROMs	Storing patient's questions and notes that they want to bring up in their clinic visits	User: #NOTE: Remember to ask doctor about controlling my blood sugars when exercising User: #NOTE: How to apply for ADP User: #NOTE: Mental health resources at clinic?? KiT: Your next appointment is coming up soon, and I wanted to send you the notes you made so you can discuss them with your team: "Remember to ask doctor about controlling my blood sugars when exercising, How to apply for ADP, Mental health resources at clinic??"
PREMs/PROMs	Administering baseline and end of study questionnaire to patient	KiT: Please click on this link to complete the baseline and follow-up (6 months and 12 months) questionnaires for the study [insert REDCap link]

Table 4: Mental health crisis keywords***Standard response message (to be sent after receipt of flagged keyword)***

ONTARIO: “It sounds like you might be going through something difficult right now. If you feel like you are at immediate risk, please call 911. If not, you can always reach out to your healthcare team for support. Or to talk to someone right away, you can text HOME/ PARLER to 686868 anytime, anywhere in Canada to speak with a trained Crisis Responder through the Crisis Text Line.”

- Other Ontario mental health supports: <https://ontario.cmha.ca/provincial-mental-health-supports/>

QUEBEC: “It sounds like you might be going through something difficult right now. If you feel like you are at immediate risk, please call 911 or 811. If not, you can always reach out to your healthcare team for support. Or to talk to someone right away, you can text HOME/ PARLER to 686868 anytime, anywhere in Canada to speak with a trained Crisis Responder through the Crisis Text Line.”

- Other Quebec mental health supports: <https://amiquebec.org/crisis/>

Standard response message (French)

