If you're travelling through more than 5 time zones, you'll probably have to adjust your insulin (you'll usually need more if travelling west ← and less if travelling east → so it's a good idea to chat with your doctor about making changes to your medication dosage or schedule before you leave for your trip!)

TRAVELLING To make sure you can enjoy a stress-free trip, pack lots of extra supplies! It's good to have extra glucose meters, batteries, pumps and infusions sets, insulin and syringes (in case your pump malfunctions), and medications on hand, just in case.

You might even want to split your supplies between two bags, in case one gets lost or stolen!

SECURITY Don't worry - people living with T1D are allowed to carry medical supplies (including emergency juice above the liquid limit) with them when travelling through security! Pumps and CGMs should NOT go through an x-ray machine or body scanner, so you can ask to walk through a regular metal detector or get a pat-down instead.

You can get your doctor to provide you with a letter like this one to make the process of getting through security with your diabetes supplies smoother: <https://www.diabete.qc.ca/wp-content/uploads/2019/04/Voyage-lettreMD-Anglaisdocx-5.pdf>

Chatbot Link Appended to the End of Sample Message

Sample Q&A Answer: Thanks for asking! Hopefully this resource about food labels from Diabetes Quebec answers your question mtxt.io/cyhn5t

Appended to end of message: **If you have more questions, ask our KiT Q&A chatbot at mtxt.io/qachat?sid=12312**

Appended to the end of messages not recognized: **Hmm, looks like we don't have a good answer – sorry about that! Try our new KiT Q&A chatbot at mxtt.io/qachat?sid=12312 to see if you can find an answer there!**

Figure 1: Streamlit prototype app interface

KiT - Keeping in Touch

By using this chatbot you are consenting to its use in research. KiT is a bot, not a human. It is not a replacement for direct care. Do not use KiT to communicate urgent questions or treat medical emergencies. If you have a medical emergency call 911 immediately. KiT can make mistakes and is still under development, we recommend checking the sources of information. You should not provide personally identifiable information.

Reset Chat

 Hello, I am KiT. Just so you know, I am not real a person, just a bot. I am here to help with any diabetes questions you may have.

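### The chatbot's stated trigger for the crisis support message is suicidal ideation only, narrower than the SMS keyword rule and than the topics on which crisis-contact delivery is later checked

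*Protocol*

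**What the plan says.** The protocol describes three rules for the same safeguard.

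- **SMS.** Section 9 ties the support message to crisis texts: "If a participant texts KiT any messages signalling a crisis situation (see table 4 for list of crisis key words". The Appendix heads the message "Standard response message (to be sent after receipt of flagged keyword". The English list in Table 4 includes words for cutting, overdose, bingeing and vomiting, alongside suicide terms and methods.
- **Chatbot.** Section 9 continues: "The LLM chatbot also has instructions to send the same support messages in case any topic related to suicidal ideation is identified". No other trigger for this message in the chatbot is stated. Section 6.1.1 places the chatbot outside the SMS intervention, reached by a link, and nothing applies the Table 4 list to it.
- **Review.** Under the LLM Evaluator heading in section 9: "Conversations about sensitive topics such as mental health, crisis, suicide etc will be flagged for review by the research team within 2-4 weeks". The stated purpose is "to ensure that the bot appropriately provided the crisis info contact".

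Three further places bear on the point. When no document matches a query, section 6.1.1 gives the chatbot's standard reply as "There is no relevant information in this workspace to answer your query". The Appendix has a chatbot link that is "Appended to the end of messages not recognized". The prototype screen in Appendix Figure 1 warns "Do not use KiT to communicate urgent questions or treat medical emergencies" and tells users to call 911 in a medical emergency.

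**The concern.** Someone who texts about cutting receives the crisis line at once, because a listed word matches. If the same person writes the same thing in the chatbot, without suicidal content, the stated instruction does not require the bot to give that contact. Such disclosures are foreseeable. The intervention sends messages on coping with stressors, and Appendix Table 2 marks mental health, including eating disorders, as a prominent topic.

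The human check comes 2 to 4 weeks after a conversation is flagged. It can find that the contact was missing, but it cannot stand in for an immediate message. A staff member who finds it missing after a self-harm disclosure could not tell from the protocol whether the bot had failed or had followed its rule.

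**Working it through.** The point turns on the scope of a rule, so the main check is to set the texts side by side.

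| Rule | Place | Scope stated |
|---|---|---|
| SMS support message | Section 9; Appendix Table 4 | Messages signalling a crisis, detected by keyword; the list includes cutting and overdose |
| Chatbot support message | Section 9 | Topics connected with suicidal ideation |
| Review of crisis-contact delivery | Section 9, LLM Evaluator | Mental health, crisis, suicide and similar |

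1. *Does the SMS rule reach the chatbot?* No place says so. The SMS rule concerns what participants text to KiT, and the chatbot runs in a separate web app.
2. *Is another trigger for the contact stated for the chatbot?* No. The English Safety Testing text mentions firmer advice to attend an emergency department, in cases it does not define, and an explicit instruction on suicidal ideation. The latter concerns flagging questions for review and does not govern the bot's reply. Neither mentions the crisis contact.
3. *Could crisis wording be steered to the chatbot?* Yes, in principle. Texts that the SMS system does not recognise get a link to it, so wording outside Table 4 could be pointed there.
4. *What if no document is retrieved?* The stated reply carries no contact. The protocol does not say whether the crisis instruction takes precedence over it.

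**Ceiling on exposure.** The inputs are from section 8.3: expected recruits are 152 in Ontario and 114 in Quebec; after loss to follow-up they are 120 and 90. The intervention arm has 117 participants. Section 9 starts the chatbot in Ontario.

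- Ontario share of recruits: 152 / (152 + 114) = 152/266 = 57.1%.
- Ontario share after loss: 120 / (120 + 90) = 120/210 = 57.1%.
- Intervention participants in Ontario: 0.571 × 117 = 66.9, about 67.

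This assumes 1:1 allocation within sites, as the stratification in section 6.2 intends. It counts participants who could be offered the chatbot. It does not count users or disclosures. Because the chatbot was added after enrolment began, the number with access will be lower. The ceiling moves towards 117 only when the Quebec sites are added.

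**The case against.** The strongest reply is that section 9 summarises a prompt that is not shown. The wording is broad and at topic level, the bot sends the same messages as the SMS system, and elsewhere suicidal ideation is given as an example of sensitive content. The prompt may already cover self-harm. This stands as a limit: the documents show what the protocol states, and they do not show how the bot behaves. A reader might infer that the chatbot gives no crisis guidance after a self-harm disclosure. That is not supported, given the unseen prompt, the 911 notice and the emergency-department language.

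A second reply is that a review net wider than the trigger is good monitoring, since it catches misses. That is right. A reader might infer that the review and the trigger contradict each other, but the difference in width alone does not show this. The review asks whether the contact was given appropriately and does not require it in every flagged conversation. What remains is that delivery is checked on topics for which no instruction to deliver is stated.

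Third, Table 4 is a deliberately over-inclusive literal filter. It contains words such as train, bridge and midnight, and a language model need not copy it. This also stands, and it argues for a trigger set by topic and not by keyword.

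Fourth, the route by which a participant meets the no-information reply takes several steps. Mental-health resources are among the topics, so a document may well be retrieved. This lowers the likelihood but does not settle which instruction prevails.

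**Conclusion.** The point holds as a gap in a stated safety rule. Following section 9 exactly, a chatbot disclosure of non-suicidal self-harm, overdose or another acute mental-health crisis does not require the crisis contact, whereas the SMS rule requires it when a listed word matches. The 911 notice covers medical emergencies but gives no crisis line and is not triggered by what the participant writes. The emergency-department language is undefined in scope.

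The conclusion rests on the protocol wording alone. If the prompt is already wider, what remains is to bring the text into line with it. The number of disclosures cannot be derived. A reader might take 67 as the number affected, but it is only the exposure ceiling for Ontario. The change should be made because it is a cheap gain in participant safety; the point has no bearing on the validity of the primary analysis. Confidence is medium.

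**What to change.** In section 9, state the chatbot trigger by topic: suicidal ideation, self-harm, overdose or acute mental-health crisis. Leave out general distress, stress and burnout, which KiT is meant to support with coping content. State that this instruction overrides the no-relevant-information reply in section 6.1.1. Add a few questions on these topics to the French safety testing, which is still pending.

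The cost is one or two sentences of protocol text, a small prompt change if the prompt is not already this wide, and a few extra test questions. The downside is that some support messages will go to participants who do not need them. The SMS keyword list already accepts that cost.

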4.2 SCIENTIFIC RATIONALE FOR STUDY DESIGN

We chose to conduct a multi-site randomized control trial in both Ontario and Quebec in order to ensure representation across the two main sizes of pediatric diabetes centers (tertiary and community); our intervention will also be available in both English and French; participants in both provinces will be able to select their preferred language of intervention delivery at study enrollment. We opted to do 1:1, individual level randomization because the target of the intervention is individual level diabetes self-efficacy during the time between pediatric and adult diabetes care and not pediatric provider or clinic-based transition care. The treatment allocation not being blinded to the research team will not pose any bias or contamination as randomization to control or intervention group will be completed via an automated computer program on REDCap; the randomization sequence will be generated by a biostatistician who is not involved in recruitment or enrollment and has no contact with study participants. The research team does not know the randomization sequence which will be in blocks of 2 or 4, thus making it difficult to pre-determine treatment allocation during the recruitment or consent process. This study is not blinded and therefore the research team, Memotext and participant will know which arm they have been randomized to. Also, the control group not having access to the tailored support or diabetes resource messages will not pose any potential problems or issues as the control group and

intervention group will both be receiving the regular standard of care for diabetes and will not be restricted access to their usual diabetes resources and supports. Both the control and intervention group will receive the same incentives to complete the outcome measures at baseline, 6 months, and 12 months. The Intervention group participants may receive compensation for participation in the process evaluation upon completion of the interview.

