5 STUDY POPULATION

5.1 INCLUSION CRITERIA

To be eligible to participate in this study, an individual must meet all of the following criteria:

1. Diagnosed with type 1 diabetes, ascertained from patient's medical chart
2. Receiving out-patient care for T1D at a pediatric diabetes center participating in this study
3. Is within 6 months of either planned transfer or 18th birthday so research coordinator can approach patient and inform them about the study, and then can be re-approached for consenting and enrollment only within 3-4 months of either: planned transfer to adult diabetes care OR 18th birthday
4. Proficient in written and spoken English or French
5. Possession of their own personal mobile device that can support SMS with capacity to send and receive SMS/texts
6. Valid and working mobile phone number
7. Valid email address

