- 8) The local coordinator will randomize the participant using REDcap's automatic randomization feature. Both the local coordinator and participant will be aware of what study arm they were assigned to as local coordinator will need to explain next steps to the participant depending on study arm and participant will be aware of whether they will receive texts from the KiT intervention.
- 9) Upon randomization, the local coordinator will enter the randomized participant study ID number, randomization arm, mobile phone number, and preferred language in the Research Assistant Participant Enrollment form via Memotext.
- 10) Memotext will send an initial SMS to the participant's mobile phone number, letting them know they are now enrolled in KiT.
 - i. The following SMS will include the first URL link to a REDCap survey that first prompts to participant to complete the baseline KiT survey (demographic information and information about the participant's diabetes care and self-management). When this questionnaire is completed and submitted, the survey will automatically produce the next surveys for participant completion, one at a time: READDY tool questionnaire, SEDM, and BDA Stigma subscale
 1. Some of the content and sequence of the messages and resources sent to the intervention participants will be personalized, based on confidence ratings as measured by the "Readiness of Emerging Adults with Diabetes Diagnosed in Youth" (READDY) tool.
 2. For all participants, if they do not complete the questionnaires within 1 week of receipt, KiT intervention will send a follow-up reminder SMS asking them to complete the questionnaire. This reminder will be sent a maximum of two times (1 week apart). At week three, the local research coordinator will be notified via email by Memotext that the participant has not yet completed their questionnaires and will then follow up with the participant via telephone, SMS or email asking them to complete the questionnaires.
 3. Once the participant completes the questionnaires, they will be sent their \$20 Amazon gift-card via SMS.
 - ii. If the participant is in the intervention arm, after they complete the baseline questionnaires, they will then be sent an SMS with a link to a short enrollment survey where they will learn how to use KiT, access the settings, set up their frequency preferences to receive the content, and set up appointment reminders.

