- 3) Provide participant compensation for filling out questionnaires about clinic attendance, information about diabetes care and self-management such as diabetes device use and measures of glycemia, and patient reported outcome measures (READDY, BDA Stigma subscale, and SEDM; all at baseline, 6 months and 12 months). All participants (in both the control and experimental groups), will be provided the same compensation at the same time-points once all outcome measures at each time-point (baseline, 6 months and 12 months) have

been completed: a \$20 Amazon gift-card for completion of outcome measures at each time-point for a maximum total value of \$60 in Amazon gift-cards per participant. This compensation amount was determined based on the total estimated time to complete all outcome measures (total of 4 outcome measures plus initial survey) at each time-point – approximately 15-20 minutes. This compensation amount per time-point is further justified as other similar studies in the same population offered \$20 for completion of 8-10 outcome measures that took approximately 45 minutes to complete. When KiT sends messages with links to the REDcap-based outcome measures, KiT will also remind participants that they will only receive an automatic e-gift card via KiT text-message once they complete all questionnaires at each time-point.

- 4) Question and Answer (Q&A) feature: participants in the intervention arm can message the KiT intervention with their T1D related questions and the intervention will send links (where available) via text-message, to relevant resources from the validated resources collected in the environmental scan.
- 5) LLM Chatbot feature: in addition to the Question and Answer (Q&A) feature, participants in the intervention arm can also access a LLM chatbot via a link KiT shares that is outside of the SMS-based intervention. Participants can ask the LLM chatbot their T1D related questions and the LLM chatbot will send answers in a natural language format and links (when available) from the same validated resources collected in the environmental scan. If no resource relevant to the question is found, a message stating this is presented to participants.

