patient partners) to score the answers from 1-5 based on accuracy, safety and a metric known as the global quality score. The validity and reliability of these metrics were established during several rounds of testing with the raters in addition to literature evidence. The LLM chatbot is not a learning model and will only utilize existing resources gathered for the KiT study. Although, since LLMs are stochastic in nature – i.e., may generate different answers to the same question at different times – we will ask each question 3 times. In addition, we want to test the use of LLMs as evaluators of the quality of answers. In order to do this, we will ask an LLM evaluator to also grade the answer to questions based on the aforementioned criteria, and compare this rating to the human raters. If successful, we plan to have the LLM evaluator continuously assess the questions asked by participants for any sensitive information (e.g., pertaining to suicidal ideation) and the quality of answers given, and flag any potentially harmful case for human review during the study.

It should also be noted we have previously assessed a prototype version of the KiT LLM and an LLM Evaluator (using GPT-4 accessed through UHN's Microsoft Azure subscription) on a set of synthetic questions, with promising results. We are in the process of improving these applications based on feedback from this initial assessment. Examples of these updates include stronger language on recommending visits to the emergency department in certain cases and explicit instructions to consider suicidal ideation when flagging potentially sensitive questions. We plan to test updated versions of the KiT and Evaluator LLMs with the questions already asked by participants during the study.

The English safety testing has been completed and the results are below. Once this amendment is approved them the LLM chatbot will be incorporated in Ontario sites.

English safety testing conclusions (please see accompanying PowerPoint presentation in CTO application)

Common questions to all raters (39 participant questions +12 synthetic questions)

- When considering the full set of questions (39 participant, 12 synthetic), the KiT LLM seems to perform well, with high scores in most metrics, particularly Safety.
- Overall the LLM Evaluator seems to act as, or more, conservative than most human raters (the exception being Patient Partner 2, which was slightly more conservative in general).

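### The LLM chatbot is safety-tested by language but released by province, so nothing written withholds it from French-language Ontario participants before French testing is done

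*Protocol*

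**What the plan says.** **Language is the participant's choice at every site.** Section 5.1 admits anyone "Proficient in written and spoken English or French", without reference to province. Section 4.2 adds that "participants in both provinces will be able to select their preferred language of intervention delivery at study enrollment". At step 9 of the onboarding process in Section 5.4, the local coordinator enters study ID, "randomization arm, mobile phone number, and preferred language in the Research Assistant Participant Enrollment form via Memotext".

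**The chatbot is offered to the whole intervention arm.** Section 6.1.1, item 5, states that "participants in the intervention arm can also access a LLM chatbot via a link KiT shares that is outside of the SMS-based intervention". The same section has the URL sent by SMS. The Appendix shows the link appended both to Q&A answers and to replies sent when KiT does not recognise a message.

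**Testing is organised by language.** Section 9 (Participant Safety) first says that "the LLM chatbot feature will not be turned on until the English safety testing and analysis are completed". It then reports the English results, and gives the reason for a second round: "As our study is in English and French, it is important for us to complete the safety testing in French as well".

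**Release is organised by province.** For Ontario: "Once this amendment is approved them the LLM chatbot will be incorporated in Ontario sites". For Quebec: "an amendment will be submitted once the French safety testing and analysis is completed prior to implementation in Quebec sites".

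**The concern.** The safeguard and the release rule use different units. The stated reason for French testing is that the study runs in two languages, yet the rule that applies it refers to Quebec sites. A participant who chose French at an Ontario site falls between the two: released by province, not yet tested by language.

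Three functions would be running without a French test for such a participant:

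- the accuracy and safety of the chatbot's answers;
- its recognition of suicidal ideation in a French conversation, which Section 9 leaves to instructions given to the LLM;
- the LLM evaluator's flagging. Section 9 sends flagged sensitive or low-safety conversations to human review within 2-4 weeks, while unflagged conversations may wait for an interim look or the end of the study. A failure to flag in French could therefore go unseen for a long time.

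The testing is not a formality. Even in English, one patient-partner rater recorded a few major safety concerns.

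**Working it through.** No sample-size, power or event figure bears on this point, so the check sets the rules side by side.

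**Step 1. Is language tied to province anywhere?** No. Sections 4.2 and 5.1 leave it to the participant at all sites.

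**Step 2. Does any section restrict the link by language?** No. Section 6.1.1 gives access to the intervention arm as a whole and describes one web app, with no language setting or separate language version. The Appendix examples of the appended link carry no language condition.

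**Step 3. Are French-language Ontario users foreseen?** Yes. Appendix Table 4 contains a French crisis message written specifically for Ontario.

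**Step 4. Cross the two rules.** For the period after Ontario release and before French clearance:

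| Site | Chosen language | Release rule as written | Tested in that language? |
|---|---|---|---|
| Ontario | English | Released | Yes |
| Ontario | French | Released | **No** |
| Quebec | French | Held | No |
| Quebec | English | Held | Yes |

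The province rule and the language test disagree in two of the four cells. Quebec/English is only a delay. Ontario/French is the safety gap.

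**Step 5. Who is in the gap?** Only French-language Ontario participants in the intervention arm whose 12 months overlap the interval between Ontario release and French clearance. The chatbot arrives by amendment after the Q&A feature was already in use, so anyone who finished before switch-on is not exposed. Nor is anyone who enrols after French clearance.

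**Step 6. How many?** The documents do not allow an estimate. They give no language split and no date for French testing or its approval. The one related fact is the statement in Section 9 that the Q&A feature had received no French participant questions. That suggests little French use at the time of writing. It does not show that nobody had chosen French, or that nobody will while enrolment continues under the same rule.

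**The case against.** The strongest reply is that Section 9 can be read as releasing only the tested English version in Ontario. The Ontario sentence stands under the English testing heading, and the French paragraph shows that the team knows French needs its own test. A filter may already operate without being written down. That cannot be excluded, and it limits what can be claimed: the defect shown is an unwritten restriction, not an observed exposure. It does not remove the point, because the written rule names sites and the access text names the whole arm.

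A reader might also infer more than the documents support:

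- *That every French-language Ontario intervention participant is exposed.* The mid-trial switch-on and the 12-month participation period rule this out.
- *That the crisis message itself is untested in French.* The text is fixed and already written in French for Ontario, and Table 4 also has French keywords for the SMS system. What lacks a French test is the LLM's detection, its answers and the evaluator's flagging. The app's opening notice also directs emergencies to 911.
- *That the safeguard fails generally.* For French-language participants at Quebec sites it works as written.
- *That English-language Quebec participants are wrongly denied the chatbot.* Holding back an optional feature until a further amendment is a permissible staging choice, and they keep the Q&A feature, which draws on the same resources.
- *That release by site damages the trial comparison.* Randomization is stratified by site (Section 6.2), and the primary analysis compares the arms regardless of original or modified intervention (Section 8.5.2). Chatbot conversations are logged with timestamps by study ID. Release by language would not clearly be easier to interpret.

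**Conclusion.** The point holds as a gap in a written safety rule. Followed literally, the protocol opens the chatbot to French-language intervention participants at Ontario sites before the French test that it calls important. The conclusion rests on two statements in the text (language chosen in both provinces, release by province) and on the absence of any language condition on access.

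The group may be small and the gap is temporary, though no end date is given. The case for acting rests on the kind of failure, since crisis detection and the monitoring meant to catch bad answers are both involved, and on how little the correction costs. It does not rest on a head count. The documents do not show that any French-language Ontario participant has received the link, and the primary endpoint is not at issue.

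**What to change.** Reconcile Section 4.2 with the two release statements in Section 9 by adding a condition to the Ontario rule, for example:

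> Until French safety testing is complete and the corresponding amendment is approved, the chatbot link, including the link appended to Q&A replies and to replies to unrecognised messages, is sent at Ontario sites only to intervention participants whose recorded preferred language is English.

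The Quebec rule need not change. If the filter already operates, the sentence simply records it. If the chatbot is already live in Ontario without it, the filter should be applied promptly.

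**Cost.** One sentence in the protocol, and one filter on a field that the coordinator already enters in the Memotext enrolment form. French-language Ontario participants wait for an optional feature and keep the existing Q&A in the meantime. The filter acts on recorded preference, so it does not stop an English-preference participant from typing in French.
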